## 1. Background and general remarks

Axial spondyloarthritis (axSpA) and psoriatic arthritis (PsA) are the main diseases in the group of rheumatic conditions called spondyloarthritis (SpA). AxSpA itself comprises of ankylosing spondylitis (AS) and the newly defined subgroup non-radiographic axial SpA (nr-axSpA). The estimated prevalence rates are 0.8% for axSpA and 0.2% for PsA corresponding to about 550.000 axSpA patients and 140.000 PsA patients in Germany [1].

The treatment of axSpA and PsA has been revolutionized by the introduction of targeted therapies since 2003. Today, about half of the patients with ankylosing spondylitis (AS) treated in Germany by rheumatologists receive any of these drugs [2], in PsA the percentage is about 30% (DRFZ, unpublished data from the National Database, 2014). However, the safety and effectiveness of these newer treatments has not been sufficiently explored under real-life conditions so far. The various European registers have only rarely published results on this group of diseases. They mainly refer to drug survival and effectiveness. Comparing drug survival in axSpA, PsA and rheumatoid arthritis (RA), better retention rates compared to RA were found for both forms of spondyloarthritis in the Spanish [3] as well as in the Norwegian registers [4].

The British register reported high drug survival rates in PsA, even after failure of a first TNF inhibitor (TNFi) and switching to a second TNFi [5]. Clinical response and drug survival in PsA were also investigated by the Danish biologics register DANBIO showing lower response to the second TNFi after switching [6]. For PsA, a reduction in work disability after initiation of TNFi [7] and improvements in overall quality of life were shown [8].

In AS, most of the reports also pertain to drug survival and effectiveness: The Swedish register compared drug survival in a total of 2,520 patients with AS or undifferentiated spondyloarthritis and found better drug survival of the first TNFi in combination with csDMARDs [9]. The South Swedish register also found high drug survival rates on TNFi in patients with AS, specifically in males and those with peripheral arthritis [10]. The Finnish register reported equal effectiveness but better drug survival for etanercept and adalimumab compared to infliximab in 543 AS patients [11].

A recent Cochrane review found moderate to high quality evidence that anti-TNF agents improve clinical symptoms in the treatment of AS. The evidence concerning serious adverse events was limited to clinical trials with short duration. Using indirect comparative methodology inconclusive results have been found about differences between anti-TNF agents in terms of the key benefit or harm outcomes [12].

There is very limited real-life evidence concerning the safety of biologic and other targeted therapies in axSpA and PsA [13,14]. The British register BSRBR reported overall safety of TNF inhibitors in 596 PsA patients compared to seronegative RA [15]. The Swedish register ARTIS analysed lymphomas in patients with PsA or AS exposed to TNFi in comparison with the normal population [16].

In addition to these registers covering different rheumatologic diseases, some SpA specific registers/cohorts were established [17-20]. Publications from these registers are, however, limited and focus on the disease course in AS.

In summary, there are some reports on effectiveness but very limited information on the safety of biologic agents in axSpA and PsA. Importantly, nearly all reports lack adequate control groups so far. Furthermore, the development of new classification criteria for axial SpA in 2009 led also to the new diagnostic entity axial SpA which includes AS and the so-called non-radiographic axial SpA (nr-axSpA) [21,22]. Especially for the latter group of patients there is a strong need for valid data on the disease course and the long-term safety profile of applied treatments.

In contrast to axSpA and PsA, there is a wealth of information on targeted therapies in RA resulting from the different European biologics registers [23]. The close connection between features of the disease, the immunosuppressive properties of treatments, co-morbidity and various outcomes has been consistently shown. However, despite intensive research, many questions, specifically concerning high-risk patients and outcomes with long latency, remain to be answered even in RA. All the more this applies to axSpA and PsA: Due to large differences in the age and sex distribution, in risk factors, the spectrum of co-morbidities and co-medications, results on safety and effectiveness of treatments cannot be robustly transferred from RA to axSpA or PsA. Both disease entities of the group of spondyloarthritis have to be investigated separately since, for instance, risk factors and co-morbidities in PsA significantly differ from RA on the one hand and from axSpA on the other. In addition, benefits of treatment may be different from RA, e.g. due to NSAID reduction or improvements in work ability. Risks may be different due to other co-morbidities, specifically in PsA. Further, there is a specific lack of knowledge on the course of non-radiographic axSpA and the outcome of treatments.

The German biologics register RABBIT (“Rheumatoide Arthritis - Beobachtung der Biologika-Therapie”) is among the largest biologics registers on RA in the world. It has been conducted as an independent long-term observational cohort study of the safety and effectiveness of biologic agents in RA since 2001. RABBIT-SpA, the disease register for axial spondyloarthritis and psoriatic arthritis, follows the concept of RABBIT. It is conducted as an open-ended, disease-specific prospective long-term observational cohort study. For methodological reasons, inclusion into the disease registry is linked to the start of a new treatment.

RABBIT-SpA observes patients treated with biologics, biosimilars, or other new targeted therapies licensed in Germany for the treatment of AS, nr-axSpA or PsA, together with conventional treatments. The respective current index drugs are listed on the project website [www.rabbit-spa.de](http://www.rabbit-spa.de). In case of changes, this list will be updated immediately. The control therapies are all other conventional treatments for axSpA or PsA. The aim is to establish robust evidence on the long term outcomes of SpA, as well as effectiveness, long-term safety, and costs of the treatments under real-life conditions.

In order to ensure sustainable support for the conduct of the study, RABBIT-SpA is funded jointly by pharmaceutical companies with licensed biologic or other targeted agents for the treatment of axSpA or PsA. For that purpose, a joint contract has been made between the German Rheumatism Research Centre (Deutsches Rheuma Forschungszentrum DRFZ) and all funding companies. Further targeted therapies and the respective companies can access the study under the following conditions:

- the drug is licensed in Germany for the treatment of axSpA or PsA,
- the principal investigators, advisory board, and the pharmaceutical companies already funding RABBIT-SpA agree to include the new substance as index drug, whereby participation should not be denied without good reason,
- the pharmaceutical company responsible for the new drug accesses the existing contract and makes an appropriate contribution to the joint, unconditional grant for the study,

## **2. Aims of the study**

Major aims are:

1. To describe the long-term effectiveness of treatment with targeted therapies, e.g. drug survival, effectiveness of treatment combinations, level of disease activity achieved.

2. To study the long-term safety of all available targeted therapies for axSpA and PsA  
This includes the observation of all adverse events (serious and non-serious) in order to assess the overall safety profile. Specific emphasis will be laid on “events of interest” (see 8.1.1 below).
3. To investigate the interplay between disease activity, comorbid conditions and safety outcomes, the interplay between disease activity, radiographic changes and functional outcomes and to explore the role of treatment in these interactions.
4. To describe selected direct and indirect costs of targeted therapies compared to standard therapy. This includes the description of health care consumption and work disability.

### **3. Study leadership and Scientific Advisory Committee**

The scientific responsibility and study leadership is held by the German Rheumatism Research Centre Berlin, Programme Area Epidemiology, Pharmacoepidemiology Group (Head of Pharmacoepidemiology Group: PD [name], Deputy Head of Pharmacoepidemiology Group: PD [name]). The principal investigators of RABBIT-SpA are PD [name] and PD [name]. The leading statistician is [name]. The responsibility of the study leadership comprises study design, data storing, data protection and security, monitoring, statistical analyses, preparation of reports, publication of results and representation of the study in the scientific community.

RABBIT-SpA has a Scientific Advisory Committee (SAC) which oversees the register. The SAC members are distinguished experts in the fields of axSpA and PsA. They are nominated by the study leadership in agreement with the sponsoring companies. A nomination period will be three years, re-nomination is possible. For the first three years the following persons were nominated and agreed: PD [name], Frankfurt, [name]. [name], Herne, [name], Berlin, [name]. [name], Erlangen, and [name]. [name], Berlin. Twice a year, joint meetings of the SAC, the study leadership and up to two (one substance under observation) or up to three representatives ( $\geq$  two substances under observation) from the companies are held. In these meetings, the PIs report on the current state of the register and present future data analyses.

In order to pre-empt any conflict of interests, the members of the SAC do not receive any remuneration from the companies for their participation in RABBIT-SpA.

### **4. Study Design**

RABBIT-SpA is a prospective observational cohort study. The rules of good pharmacoepidemiological practice are followed [24]. Physicians aiming at taking part in RABBIT-SpA must sign a contract with the DRFZ. The aim is to observe each patient for at least five years, if possible, for ten years.

Patients enrolled will have the following visits: baseline, months 3, 6, 12, 18, 24, 30, 36, 42, 48, 54, 60. If the patient agrees, the observation will be prolonged with visits at 66, 72, 78, 84, 90, 96, 102, 108, 114 and 120 months.

There is no influence on any treatment decision from the principal investigators, scientific advisory board or pharmaceutical companies sponsoring the study. The type of the treatment administered, and the conduct of individual therapy is determined by the treating physician only.

### **5. Inclusion criteria**

Inclusion criteria are:

- Signed informed consent
- Diagnosis of axial spondyloarthritis or psoriatic arthritis
- Age at inclusion  $\geq 18$  years
- Cases: starting treatment with one of the index drugs
- Controls:
  - start of a new systemic standard therapy after failure of at least one systemic standard therapy (systemic standard therapy includes NSAIDs, csDMARDs)
  - clinically relevant increase in the NSAID dose

## 6. Assessments and evaluation methods

The following outcome measures will be investigated:

### Effectiveness and cost components

1. Treatment survival and reasons for discontinuation
2. Course of the disease (e.g. change in disease activity parameters, function and general well-being)
3. Radiographic and MRI outcomes
4. Days in hospital
5. Medication, non-pharmacologic therapies and joint surgery
6. Days off work in employed patients
7. Early retirement and return to work (working days gained)

### Safety

1. Occurrence of adverse events (serious/non-serious)
2. Outcome of pregnancy
3. Mortality

### Flow chart of parameters investigated

	ax-SpA	PsA	Study entry	At 3 months	Frequency of f/u
Physician					
Inclusion criteria	x	x	x		
Demographics (year of birth, gender)	x	x	x		
Diagnosis/disease duration/1st symptoms	x	x	x		
Health insurance	x	x	x		
Diagnostic symptoms/ASAS criteria	x		x		
Chronic inflammatory back pain	x		x		
CASPAR-classification		x	x		
Type of PsA manifestation		x	x		Every 12 months
Imaging – radiographic findings	x	x	x		Every 12 months
Physician global disease activity	x	x	x	x	Every 6 months
Height	x	x	x		
Weight	x	x	x		Every 12 months
Extent (hip, waist)	x	x	x		Every 12 months
CRP	x	x	x	x	Every 6 months

BSG		x	x	x	Every 6 months
HLA-B27	x	x	x		Every 12 months
RF / ACPA		x	x		Every 12 months
Lumbal lateralflexion	x		x		Every 12 months
Schober	x		x		Every 12 months
Arthritis (joint counts)	x	x	x	x	Every 6 months
Enthesitis	x	x	x	x	Every 6 months
Coxitis	x		x		
Joint replacements	x	x	x		Every 12 months
Vaccination	x	x	x		Every 12 months
Extraarticular manifestations	x	x	x	x	Every 6 months
Comorbidity/comedication	x	x	x		Every 12 months
Current therapy for SpA/PsA (systemic and topic)	x	x	x	x	Every 6 months
Glucocorticoids (systemic and local injections)	x	x	x	x	Every 6 months
Other therapies	x	x	x	x	Every 6 months
Previous therapies	x	x	x		
% body surface affected by psoriasis		x	x	x	Every 6 months
Pregnancy	x	x			Every 12 months
Adverse events	x	x		x	Every 6 months
Patient					
Patient global health status (NRS)	x	x	x	x	Every 6 months
Patient global disease activity (NRS)	x	x	x	x	Every 6 months
Sleep disturbances (NRS)	x	x	x	x	Every 6 months
BASDAI/BASFI	x		x	x	Every 6 months
ASAS HI	x		x		Every 12 months
HAQ/PSAID		x	x	x	Every 6 months
DLQI		x	x		Every 12 months
WHO-5	x	x	x		Every 12 months
PASS	x	x	x		Every 12 months
Patient satisfaction	x	x	x		Every 12 months
Smoking status	x	x	x		
Currently smoking	x	x	x		
Physical therapy	x	x	x		Every 12 months
Sport	x	x	x		Every 12 months
Level of education	x	x	x		
Work status	x	x	x		Every 12 months
Sick leave / Physician contacts / hospital admissions	x	x	x		Every 6 months
Work activity index (modified WAI)	x	x	x		Every 12 months
Adherence to prescribed medication	x	x	x		Every 12 months
Patient organisation	x	x	x		

Radiographs and MRIs will be uploaded at baseline and at follow-up, if available.

## 7. Adverse events

### 7.1. General procedures

Adverse events (AE) and serious adverse events (SAE) are recorded according to the ICH guideline on clinical safety data management: definitions and standards CPMP/ICH/377/95/E2A. Therefore, any

untoward medical occurrence observed in a patient has to be reported as AE. The AE does not necessarily have to have a causal relationship to the treatment of the patient. Any AE that results in death, is life-threatening, requires inpatient hospitalization or prolongation of existing hospitalization, results in persistent or significant disability/incapacity, is a congenital anomaly/birth defect, or other medically important condition according to CPMP/ICH/377/95/E2A has to be reported as SAE. In addition, pregnancies have to be reported as serious adverse events. These definitions of AEs and SAEs are also provided in the CRFs. Physicians will be asked to appraise the possible causal relationship to drugs applied. Brand names need to be reported in the case of index drugs. Furthermore, physicians will grade all AEs in “mild”, “moderate” or “severe” according to the recommendations of the OMERACT Toxicity Working Group.

## **7.2 Events of interest**

In agreement with all companies funding RABBIT-SpA, a number of “events of interest” which require specific attention were defined. They are:

- tuberculosis
- other serious infections (e.g. pneumonia, infections of the CNS, septicemia, bone or joint infections, opportunistic infections)
- congestive heart failure
- myocardial infarction
- stroke
- central demyelination
- serious hematologic disorders (e.g. bone marrow depression and hypoplastic anemia)
- neoplasms (lymphomas, solid malignancies, other neoplasms)
- serious systemic hypersensitivity reactions / serious infusion reactions
- hepatic failure
- serious gastrointestinal ulcer/perforation
- Crohn's disease
- colitis ulcerosa
- uveitis
- pregnancies
- deaths
- reversible posterior leucoencephalopathy syndrome (RPLS)
- renal failure
- progressive multifocal leukoencephalopathy
- Stevens Johnson syndrome (SJS) /toxic epidermal necrolysis (TEN)
- suicidal ideation/behavior
- interstitial lung disease (ILD)

Frequencies and crude incidence rates of these events of interest will be reported regularly (see 7.4). Changes of the list above have to be based on an agreement between the pharmaceutical companies funding RABBIT-SpA and the principal investigators.

## **7.3 Safety reporting**

For all serious adverse events of interest, additional information, specific for the respective events, which is not part of the regular e-CRF is requested from the treating physician. Corresponding

queries will be generated automatically directly after saving the SAE of a patient into the RABBIT SpA database. Unique transaction keys will automatically be generated to allow an unambiguous assignment between SAEs reported in the e-CRF, automatically generated query forms, and possible additional medical reports with more detailed information on the SAE. Additional medical reports will be send by fax to the study center. The treating physician is responsible for data protection (e.g. to blacken personal data) in such cases. Additional information not part of the e-CRF is also requested for all other SAEs which are according to the assignment of the treating rheumatologist possibly related to an index or control treatment. SAEs with missing assignment of the causal relationship are considered as possibly related. The results of these queries are sent out to every company marketing the possibly related index drug. Additional information received for the control drugs are collected in the DRFZ.

The IT platform allows direct access to SAE queries and transfers these data into a separate SQL database in the study center. The SAE will be coded using the Medical Dictionary MedDRA from trained staff at the study center on the MedDRA preferred term level. Following the coding process the study center will send a first notification to the respective company of the index drug.

After receipt of the SAE specific query and, if available, the medical reports, the information in the separate SAE database will be completed and a second notification will be send to the respective company.

Documenting SAEs and related non-serious AEs on the physician report form does not release the treating physician from his/her responsibility to notify the Bundesamt für Arzneimittel und Medizinprodukte (BfArM) (German regulatory authority) or the Paul-Ehrlich-Institut of any adverse drug reactions in accordance with the professional code of conduct.

#### **7.4 Six monthly reports**

Every six months each pharmaceutical company funding RABBIT-SpA will receive a report which contains detailed records on each particular SAE (events of interest and other SAE) which occurred during the 6 months period and which were assigned to their index drug in the licensed indications covered by this registry. The report comprises also all SAEs assigned to control treatments. Except for deaths and malignancies an SAE is assigned to all index drugs a patient received during the last 3 months before the onset of the SAE (3-months risk window). SAEs which cannot be assigned to one of the index drugs according to this rule are assigned to control treatment. This approach with equal risk windows for different drugs will be used for feasibility reasons. In contrast, malignancies and deaths will be assigned to all treatments the patient was ever exposed to during the observation in RABBIT-SpA. The assignments are not connected with a conclusion about a causal relationship.

In addition to the detailed reports of SAEs the companies funding RABBIT-SpA will receive summary reports comprising crude cumulative incidence rates of events of interest and their 95% confidence intervals for their own drugs and for the control groups. The so called "Manchester template" is used to report the event rates. This "Manchester template" was defined and harmonized between the British, Swedish and German RABBIT biologics register and includes incidence rates of the total number of all observed SAEs.

Detailed multivariate analyses cannot be provided every six months, but will be done in scientific investigations and published in international journals.

Furthermore, summary reports of non-serious AEs assigned to an index drug of the company will be contained in the six months reports. If required by the respective company, these AEs will be grouped into mild, moderate, or severe AEs.

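### The 3-month assignment window in section 7.4 has no exception for congenital anomalies or late pregnancy outcomes, so when dated at birth they are not counted under an index drug stopped in early pregnancy

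*Protocol*

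**What the plan says.** Section 7.4 (Six monthly reports) sets the general rule: "Except for deaths and malignancies an SAE is assigned to all index drugs a patient received during the last 3 months before the onset". The remainder has a default: "SAEs which cannot be assigned to one of the index drugs according to this rule are assigned to control treatment". Two event types follow an ever-exposed rule instead: "malignancies and deaths will be assigned to all treatments the patient was ever exposed to during the observation in RABBIT-SpA". The reason given for a common window is practical: "This approach with equal risk windows for different drugs will be used for feasibility reasons". The section also limits how the result may be read: "The assignments are not connected with a conclusion about a causal relationship".

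Pregnancy enters the protocol in four places:

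- Section 7.1 counts as serious any event that "is a congenital anomaly/birth defect, or other medically important condition".
- Section 7.1 also requires every pregnancy to be reported as an SAE.
- Section 7.2 names pregnancies among the events of interest. Congenital anomaly is not named there.
- Section 6, under Safety, lists "Outcome of pregnancy" as an outcome to be investigated.

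No passage says what date counts as the onset of a congenital anomaly, a stillbirth or a preterm birth. None says whether the birth outcome is recorded on the pregnancy SAE or as a new SAE.

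**The concern.** A window counted back from onset suits events that follow exposure closely. For a congenital anomaly, the exposure of interest lies around conception and in early pregnancy, while the event is usually recorded at delivery. Counting 3 months back from delivery covers late pregnancy only. A drug stopped once the pregnancy was recognised is outside the window, and a drug first given late in pregnancy is inside it.

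The default rule makes this more than a gap. The event is not left unassigned: it is added to control treatment, or to whichever index drug was given later. The column for the drug used in early pregnancy is too low and another column too high. If that other column is control, the contrast a company sees between its own drug and control is distorted in the drug's favour.

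The protocol already accepts that one window does not fit every event type, since it exempts malignancies and deaths. The feasibility reason supports equal windows across drugs. It does not explain why all other event types share one anchor date.

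**Working it through.** The protocol gives no figure on this point to reproduce. The check is date arithmetic.

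**Inputs from the protocol.** Window of 3 months before onset, exceptions for deaths and malignancies only, and default to control treatment (all section 7.4).

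**Assumptions not in the protocol.** Gestational age is counted in weeks from the last menstrual period. The index drug is last given at week 4 to 12. Birth is at week 28 to 40. The outcome is a separate SAE dated at birth.

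**Window length.** 3 × 30.4375 / 7 = 13.04 weeks.

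**Condition for assignment.** Event week − week of last exposure ≤ 13.04. The earliest last-exposure week that is still assigned is therefore event week − 13.04.

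| Birth at week | Drug must be given at or after week | Gap if stopped at week 4 | Gap if stopped at week 12 | Assigned? |
|---|---|---|---|---|
| 40 | 27.0 | 36 weeks (8.3 months) | 28 weeks (6.4 months) | no |
| 37 | 24.0 | 33 weeks (7.6 months) | 25 weeks (5.7 months) | no |
| 34 | 21.0 | 30 weeks (6.9 months) | 22 weeks (5.1 months) | no |
| 28 | 15.0 | 24 weeks (5.5 months) | 16 weeks (3.7 months) | no |

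Every combination fails, including a birth at week 28 after stopping at week 12 (16 > 13.04).

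**Where the rule does work.**

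- Pregnancy SAE dated at week 2: the window reaches back to 2 − 13.04 = −11.0. Dated at week 12, it reaches back to −1.0. A drug taken until the pregnancy was recognised is assigned to the pregnancy SAE.
- Loss at week 8 to 12: assigned even if the drug stopped at week 0 (12 − 0 = 12 < 13.04).
- Loss at week 16: assigned if the drug stopped at week 4 or later (16 − 4 = 12), but not if it stopped at week 0.
- Loss at week 20: assigned if the drug stopped at week 8 (gap 12), but not at week 4 or 6 (gaps 16 and 14).

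The failure is therefore confined to later events. For a drug stopped at week 4 it starts after about week 4 + 13.04 = 17; for one stopped at week 8, after about week 21.

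**Do the pregnancy and the birth fall in one report?** With the pregnancy dated at weeks 5 to 8 and birth at weeks 37 to 40, they are 37 − 8 = 29 to 40 − 5 = 35 weeks apart. A six-month reporting period is 6 × 30.4375 / 7 = 26.1 weeks. A separately reported anomaly therefore always falls in a later report than the pregnancy SAE, and the section 7.4 rule is applied to it afresh.

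**The case against.** A reader might infer that a drug stopped early is never linked to the birth outcome, that its company would not see the case, and that the register cannot study pregnancy outcomes. The documents do not support any of these:

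- The pregnancy is an SAE in its own right and is normally assigned to the early drug. As an event of interest it also triggers an event-specific query under section 7.3, followed by further notification to the company. The birth outcome may be captured there.
- Section 7.3 has a route that does not use the window. Query results for SAEs judged possibly related go to the company marketing the drug, and a missing causality judgement counts as possibly related.
- Section 7.4 includes all control-assigned SAEs in every company's report. An anomaly placed under control is still visible to the company, under the wrong label. Only if the woman received another index drug within 3 months of the event would it be absent from the control listing as well.
- The window is stated for the six-monthly reports, with an explicit disclaimer on causality. Section 8.1 fixes no window for publications and requires treatment changes to be taken into account, so an analysis anchored on conception remains possible.
- The failure depends on dating the anomaly at birth, and the protocol does not say that it is dated so.

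All of this stands, and it limits the consequences. None of it corrects the section 7.4 count. The protocol does not say that the birth outcome is attached to the pregnancy record. The causality route governs queries and notifications, not the assignment in the listings. For an SAE outside the events-of-interest list, that route also depends on the physician's judgement being positive or missing. The disclaimer limits interpretation but leaves the event in the wrong column. The undefined onset is part of the defect, because the assignment depends on it.

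**Conclusion.** The point holds for the six-monthly reports. Read as written, section 7.4 assigns a birth-dated congenital anomaly or late pregnancy outcome only to index drugs given in roughly the last 13 weeks of the pregnancy. A drug stopped at weeks 4 to 12 misses that window for every birth between weeks 28 and 40. The early drug's count is then too low, and the count for control or for a later index drug too high.

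This rests on two assumptions: that the outcome is recorded as a separate SAE, and that its onset is dated at or near birth. If it is reported on the pregnancy SAE and keeps that assignment, the misplacement does not arise. Early losses are mostly assigned correctly. The number of affected cases cannot be estimated, because the protocol gives no pregnancy or anomaly rates. The problem is a misplaced count in crude reports; it does not show that a teratogenicity signal is lost to the register.

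**What to change.** In section 7.4, add congenital anomalies and late pregnancy outcomes (late loss, stillbirth, preterm birth) to the exceptions. Assign them to every index drug received from a stated interval before estimated conception until the end of the pregnancy, and tie them to the pregnancy SAE record. The sponsor should set the length of the interval and the gestational week from which a loss counts as late. The arithmetic above shows where the present window begins to fail. With this anchor, the assignment no longer depends on an undefined onset date.

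Confirm that the existing pregnancy query collects the estimated conception date or last menstrual period and the date of the last dose. Its content is not shown, so it may already do so.

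The cost is one added exception and at most two dates in an existing form. Some outcomes will be assigned to more than one drug, which the current rule already allows.

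### Section 7.4 makes control the leftover category for SAEs other than deaths and malignancies, so control rates can include past index-drug users and users of non-index targeted drugs

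*Protocol*

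**What the plan says.** Section 7.4 of the Protocol has two assignment rules.

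- General rule: "Except for deaths and malignancies an SAE is assigned to all index drugs a patient received during the last 3 months before the onset". What is left over goes to control: "SAEs which cannot be assigned to one of the index drugs according to this rule are assigned to control treatment".
- Exception: "malignancies and deaths will be assigned to all treatments the patient was ever exposed to during the observation in RABBIT-SpA".

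The same section promises each funding company "crude cumulative incidence rates of events of interest and their 95% confidence intervals for their own drugs and for the control groups", reported on a template shared with other registers. It gives feasibility as the reason for using equal risk windows and says that assignment implies no causal conclusion.

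Section 1 defines control by treatment: "The control therapies are all other conventional treatments for axSpA or PsA". It also makes the entry of a further licensed targeted drug conditional. The existing parties must agree, and "the pharmaceutical company responsible for the new drug accesses the existing contract" and contributes to the grant. A licensed targeted drug can therefore be outside the index list.

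Section 8.1 expects patients to change treatment over several years. Section 4 plans at least five years of observation and ten if possible. Section 17 lets companies use the semi-annual results for their own purposes.

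**The concern.** Sections 1 and 7.4 define control differently: one by what the patient takes, the other by what cannot be placed elsewhere. The two agree only if everyone without an index drug in the last 3 months is on conventional treatment and has had no earlier targeted therapy that matters for risk. Section 8.1 itself expects treatment to change, so that cannot be taken for granted.

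The control rate is the only comparator that section 7.4 specifies for the routine report. The adjustment principles in section 8.1 are set out for publications, and section 7.4 says multivariate analyses cannot be supplied every six months. A company that reads its own crude rate beside the control rate would take the latter as the rate under conventional treatment. On the wording it is a mixture of unknown composition, and the mixture may change as follow-up lengthens and patients stop or switch.

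**Working it through.** The protocol gives no rate, event count or power for this point, so there is no figure to reproduce. The first step is to apply the wording; the second only shows scale.

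**Step 1: where an SAE goes under section 7.4 (deaths and malignancies excluded)**

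| Patient at onset | Assigned to | Fits section 1? |
|---|---|---|
| Index drug within the last 3 months | That index drug | Yes |
| Conventional treatment, no targeted therapy during observation | Control | Yes |
| Conventional treatment, index drug stopped more than 3 months ago | Control | Not a contradiction, but past-exposed experience is mixed in |
| Non-index targeted drug, no index drug within 3 months | Control | No: this is not a conventional treatment |

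No other section provides a category for the last two rows. Section 7.4 does not say where their person-years are counted.

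**Step 2: effect on the control rate (assumed inputs)**

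Let f be the share of reported control person-time contributed by the last two rows, and k their event rate relative to the conventional-only rate. If events and person-time move together:

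reported control rate / conventional-only rate = (1 − f) + f × k

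The documents give neither f nor k. Over f = 0.1 to 0.5 and k = 0.8 to 2.0, the factor runs from 0.5 + 0.5 × 0.8 = 0.90 to 0.5 + 0.5 × 2.0 = 1.50. The reports specify no ratio, but as a reading aid a true index-versus-conventional ratio of 1.5 would appear as 1.5 / [(1 − f) + f × k]:

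| f | k = 0.8 | k = 1.0 | k = 1.5 | k = 2.0 |
|---|---|---|---|---|
| 0.1 | 1.53 | 1.50 | 1.43 | 1.36 |
| 0.3 | 1.60 | 1.50 | 1.30 | 1.15 |
| 0.5 | 1.67 | 1.50 | 1.20 | 1.00 |

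**Step 3: a possible size for f**

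From the protocol: 500 patients per index drug and two control cohorts of 1000 (section 14), five years of follow-up (section 4). Assumed: 10 index drugs, 10% of their patients' time off all index drugs, and 40% of controls switching to an index drug at year 2.

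- Off-index time: 10 × 500 × 5 × 0.10 = 2,500 person-years.
- Remaining control time: 2,000 × 5 − 800 × 3 = 7,600 person-years.
- f = 2,500 / (7,600 + 2,500) = 0.25.

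With 6 drugs and 5% off-drug time, f = 750 / 8,350 = 0.09. With 15 drugs and 15%, f = 5,625 / 13,225 = 0.43. This counts former index-drug users only; nothing in the protocol allows the non-index group to be sized.

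**Step 4: events moved, person-time not moved**

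If leftover events are added to control but their person-years are not, the factor becomes [(1 − f) + f × k] / (1 − f). Even at k = 1 this is 1 / 0.9 = 1.11 for f = 0.1 and 1 / 0.7 = 1.43 for f = 0.3.

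**The case against.** The strongest case on the other side has five parts.

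- **Limited use.** The reports are crude by design and imply no causal conclusion. Section 8.1 says crude comparisons cannot be interpreted adequately, and requires publications to deal with confounding, treatment changes, selection and attrition. Companies may also request further analyses of their own products (section 9). This stands and confines the problem to the six-monthly reports. It does not correct a comparator whose label differs from its content, and the feasibility argument is made for equal risk windows, not for having no further category.
- **Former users may be proper controls.** Section 1 defines control therapies, not never-exposed patients. Someone who stopped an index drug and now takes an NSAID or csDMARD is on a control therapy. This stands: that group is a mixing of experience, not a contradiction.
- **The non-index group may be small or empty.** The index list is on a website and not in the document, and entry requires an index drug or standard therapy, so such patients would arise mainly by switching. This stands for the size, not for the wording.
- **The rates may follow another rule.** The 3-month rule is written for SAE records, and the template is not shown. Its use for the control rates is a strong inference, because the rates follow in the same section with no other rule, but it remains an inference.
- **The fix has a statistical price.** Section 8.1 expects index patients to be more severely ill, which by itself would raise a crude drug-versus-control ratio. Taking former users out of control could widen that difference in severity. This is fair, and is a reason to show the extra rows beside control and not to discard them.

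A reader might also infer that section 7.4 is what brings patients with targeted therapy before enrolment into control. It is not: section 5 admits controls at "start of a new systemic standard therapy after failure of at least one systemic standard therapy" and states no bar on earlier targeted therapy. They would be controls without the leftover rule.

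**Conclusion.** The point holds for the wording of section 7.4 and for the crude control rates built on it. One group that the rule places in control, current users of non-index targeted drugs, conflicts with section 1. Another, patients more than 3 months past an index drug, mixes past-exposed with conventional-only experience. The person-time rule is missing.

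The size is open. The factors of 0.90 to 1.50 rest wholly on assumed f and k, as does the 9% to 43% range for the share. With k = 1 and person-time moved with the events, there is no distortion.

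Two stronger readings are tempting, and the documents do not support them. A reader might infer that all SAEs are affected; deaths and malignancies, both events of interest, follow the ever-exposed rule instead. A reader might also infer that the rule necessarily masks safety signals. That needs leftover patients to be at higher risk than conventional-only patients. Section 8.1's remarks on severity and attrition make this plausible, but give no figure, and at k = 0.8 the ratio moves further from 1, not towards it.

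This is a correction to a routine report. It does not bear on the adjusted analyses planned for publication.

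**What to change.** Replace the default sentence in section 7.4 with three categories, applied in this order and to events and person-years alike:

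- (a) index drug received within the 3-month window;
- (b) current use of a non-index targeted drug, or targeted therapy during observation that now lies outside the window, reported in its own row or rows;
- (c) conventional treatment, reported as control.

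Patients in (c) with targeted therapy before enrolment can be shown as a subgroup of control. The ever-exposed rule for deaths and malignancies is not affected.

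The data are already collected: the section 6 flow chart records previous therapies at entry, and current therapy at entry, at 3 months and every 6 months. The work is a short protocol change and extra rows in the report.

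The price is a smaller control denominator. In the illustration above it falls from 10,100 to 7,600 person-years. At equal event rates, the control interval on the log scale widens by a factor of about √(10,100 / 7,600) = 1.15, with a range of √(8,350 / 7,600) = 1.05 to √(13,225 / 7,600) = 1.32.
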